## **B.** Specific Aims

Primary:

- 1. To estimate the proportion of additional infectious etiologies of febrile illness among patients presenting with an undifferentiated fever of 3 to 21 days duration.
- 2. To compare the use of antimicrobials in patients with undifferentiated fever in whom additional microbiological tests have been performed versus patients with clinical diagnosis alone.

Secondary:

- 3. To evaluate the appropriateness of the empiric antibiotic therapy based on clinical diagnosis alone and after laboratory confirmation.
- 4. To estimate the correlation between clinical diagnosis with laboratory diagnosis in patients with undifferentiated fever.
- 5. To compare the outcome among patients whose treatment is based on microbiological diagnosis compared to the patients whose treatment is based on clinical diagnosis alone.

#### 5. APPROACH: STUDY DESIGN AND METHODOLOGY

This will be a randomized, open-label, prospective study which will include patients admitted to the hospital with an undifferentiated febrile illness of 3-days or longer duration. In addition to the history, physical exam and routine laboratory tests and X-ray, when clinically indicated, a battery of laboratory investigations will be performed to identify the etiology of fever.

a. Definition of Acute Undifferentiated Fever (AUF)

Acute undifferentiated fever (AUF) will be defined as a febrile illness with a temperature of 38°C (100.4°F) or higher for at least a duration of 3 days to 21 days, which presents without an obvious cause on the basis of clinical, radiological, and rapidly available laboratory investigations, and not associated with nosocomial infection, neutropenia, or immunosuppressing conditions [12].

#### b. Study population

This study will be conducted in the inpatient ward of Patan Hospital.

Patients admitted with undifferentiated fever of at least for 3 days to 21 days duration will be enrolled in this study.

#### c. Inclusion criteria

- 1. Age 16 years or older
- 2. Documented fever (T ≥100.4F or ≥38C) of 3 days to 21 days duration
- No obvious diagnosis found on the basis of clinical, radiological, or initial routine laboratory tests\*
- 4. Admitted to the medical unit of hospital
- 5. Signed ICF (informed consent form)

(\* Initial routine laboratory tests for an etiologic diagnosis of febrile illness work up includeblood and urine cultures, malaria RDT or thick and thin smears, sputum culture and GeneXpert for MTB (if suspected on chest X-ray), and serologies for scrub typhus, dengue, Dengue, Scrub typhus, Leptospirosis, Brucellosis, Kala azar, and HIV, as indicated based on clinical picture)

#### d. Exclusion criteria

- 1. Fever of less than 3 days or more than 21 days duration
- 2. Outpatients

Principal Investigator: [name]

- 3. Patients being discharged from Emergency Room
- 4. Children (younger than 16 years in age)\*\*
- 5. Immunocompromised patients
- 6. Neutropenia (ANC <500 per cumm)
- 7. Known case of HIV infection
- 8. Admission to a hospital for 48-hours or longer within past 30 days

(\*\*Children under 16 years will be excluded since they have different causes of febrile illnesses requiring a different set of lab tests which is beyond the scope of this study.)

#### e. Informed Consent

Patients admitted to the Medical Ward with febrile illness will be screened for the study inclusion and exclusion criteria. Patients who meet all inclusion criteria and none of the exclusion criteria will be enrolled in the study after taking written voluntary consent on an Informed Consent Form (ICF) approved by the institutional research committee (IRC). If patient is unable to give consent, his or her legal guardian will be contacted for written consent on behalf of the patient.

## f. Clinical and Laboratory Procedures

The main purpose of the current study is to find additional causes of febrile illnesses in Nepal which are not tested or detected with the routine laboratory tests, and are generally labelled as an undifferentiated fever. In a patient who meets above inclusion and exclusion criteria and has undergone standard of care evaluation as listed below, the following baseline data including results of the standard of care evaluations will be collected. Then, additional lab tests as noted below will be performed to find an etiology of the febrile illness. These new tests are neither readily available nor routinely performed as a part of the fever work up in Nepal.

## Standard of Care Evaluation

Standard of care evaluation of a febrile patient is done by the treating medical team which usually consists of the following set of clinical, basic laboratory, radiological and microbiological evaluations:

- 1. History and Physical Examination
- 2. Basic Laboratory investigations: As a part of standard of care, following routine laboratory tests are done on patients with a febrile illness:

Complete blood count (CBC), Renal function test (RFT), Liver function test (LFT), CRP, ESR, Urine routine exam

- 3. Radiological investigations: Chest X-ray, USG abdomen, and other Radiological investigations (as indicated)
- 4. Microbiological investigations:
  - a. Blood cultures x 2
  - b. Urine culture/sensitivity in symptomatic patients or in patients with >10 pus cells in urinalysis
  - c. Culture of sputum, pus, and other samples as indicated based on clinical findings

d. Routine serologies- currently the following serological tests are routinely done for evaluation of fever:

HIV, Dengue, Scrub typhus, Leptospirosis, Brucellosis, Kala azar, malaria (RDT/thick and thin smears)

## Additional Evaluations for the Study

For patients without an obvious cause of fever and an inconclusive work up after standard of care evaluations, additional serological tests as a part of undifferentiated febrile illness work up will be performed, including:

- a. Clinical evaluation: includes thorough history and physical examinations based on a standard questionnaire and data collection tool
- b. Additional Microbiological Evaluations: If above listed laboratory and microbiological tests do not indicate a conclusive diagnosis, the patient's blood will be processed for additional Serological tests as a part of undifferentiated febrile illness work up. These tests will help to establish diagnosis of the following infections:
  - Murine typhus
  - Bartonellosis
  - Q-fever
  - Chikungunya
  - 7ika
  - Japanese B encephalitis
  - West Nile virus
- 5. Use of antimicrobials in the patients with and without an etiological diagnosis and their outcome at the time of discharge from the hospital will be recorded.
- g. Laboratory Methods

For the purpose of the study, following samples will be collected from 50% of randomly assigned patients for additional microbiological testing.

- 1. Blood cultures, 2 sets from 2 different sites from all study patients (20 mL total)
- 2. Serum samples for serological testing (4 mL)

After obtaining appropriate consent, total 25 mL blood will be collected from each patient assigned to the additional testing arm. Blood samples will be cultured in liquid media and held in the incubator for 7-days.

Urine will be taken to the lab for routine examination and culture will be performed only if there are >10 pus cells or patient reports urinary symptoms.

Gram stain, AFB stain and Genexpert will be performed on sputum samples.

As a part of routine febrile illness work up, the serum samples will be tested for HIV, scrub typhus, dengue, leptospirosis, brucella, malaria, and kala azar.

Additional serum sample will be processed for further serological testing for Chikungunya, Zika, *Coxiella burnetii* (Q-fever), *Bartonella henselae* (Bartonellosis), *Rickettsia typhi* (murine typhus), Japanese B encephalitis, and West Nile virus using ELISA and/or Rapid Diagnostic Test (RDT), as applicable. Although molecular tests have a higher sensitivity and specificity, molecular testing has not been planned for this study because of the budget limits.

#### h. Data collection

After taking written informed consent from patient or his/her legal guardian, data will be collected from patients who meet all of the inclusion criteria and none of the exclusion criteria. Standard questionnaires will be used and recorded on a designated laptop device protected and secured with password. Only the study data collection and management team will have access to the collected data. Physical exams and initial clinical diagnosis will be transferred from patient's chart, or by interviewing patients, if needed, using a standardized questionnaire. All available lab data and treatment (antimicrobials and other relevant therapy) will be recorded. Chest X-ray, USG, CT scan, and echocardiogram reports will be collected, if applicable to the diagnosis.

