## Preliminary work done at Patan Hospital

Patan Hospital is a tertiary care medical center with 450 beds that admits between 10 to 30 febrile patients per week depending on the season. Over 30% of these patients do not have localizing signs and symptoms for clinical diagnosis nor do they have a laboratory-based diagnosis. These cases are labelled as undifferentiated fever and receive empirical treatment with two or more antimicrobial agents. Previous studies done at Patan Hospital have demonstrated that *Salmonella typhi* and *Salmonella paratyphi A* were causes of undifferentiated fever of >3 days duration in 34% patients and *Rickettsia typhi* in 17% cases, whereas another study in 2008 found 7% cases of febrile illness has *Rickettsia typhi*, which is the cause of Murine typhus [5,6]. These studies show an increase in cases of rickettsial infections including *Riackettsia typhi* and *Orientia tsutsugamushi*. Studies at Patan Hospital have also identified *Streptococcus pneumoniae*, *Leptospira* spp., *Orientia tsutsugamushi*, Hantavirus, and *Coxiella burnetii* as casues of febrile illnesses [4-6].

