## j. Data Collection, Data Analysis and Sample Size

Demographic, clinical, radiological, and laboratory data will be collected and entered into a password protected database. To minimize the errors, data will be directly entered into the database using REDCap Database questionnaires.

Data analysis will include the followings:

- 1. Demographics and baseline characteristics of patients will be analyzed and compared between the two groups.
- 2. Clinical diagnosis and laboratory confirmation of diagnosis will be used to estimate the proportions of various infectious etiologies of febrile illness in patients presenting with a febrile illness of 3-21 days duration. (Specific aim-1)
- 3. Number, type, dose and duration of antimicrobials used to treat the patients will be collected and compared between the two groups: clinical diagnosis alone versus clinical plus microbiological diagnosis. (Specific aim 2)
- 4. Appropriateness of the empiric antibiotic therapy will be determined by an independent physician expert after the laboratory confirmation of the diagnosis. Comparison between the two groups (clinical diagnosis vs. microbiological diagnosis) will be done by calculating the proportion of cases who received appropriate antibiotics divided by the total number of cases for whom empiric antibiotics were administered. (Specific aim-3)

- 5. Pretest probability for clinical diagnosis and posttest probability after laboratory-based diagnosis will be calculated and correlated for bacterial, rickettsial, viral infections versus other causes of fever. (Specific aim-4)
- 6. Clinical outcomes will be compared for patients whose treatment is based on clinical diagnosis alone (Group 1) versus the patients whose treatment is based on clinical plus microbiological diagnosis (Group 2). Composite Positive outcome (complete or partial recovery) and Negative outcome (in-hospital death) will be compared between the two groups. (Specific aim-5)

Demographics and baseline characteristics of patients will be expressed in percentages, means±SD, 95% confidence intervals, and/or median±IQR, as appropriate. Proportions will be compared between the two groups with Chi-square tests. Numerical variables will be expressed as Means/SD/95% confidence intervals and Median/IQRs, whereas Student T test or Mann-Whitney test, respectively, will be used for statistical comparisons. Alpha will be set at 95% (level of significance, p <0.05).

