## 6. PROTECTION OF HUMAN SUBJECTS (ETHICAL CONSIDERATIONS)

This clinical research project will be submitted for a full board approval by the PHAS Institutional Research Committee. Patients will be enrolled from Patan Hospital's inpatient ward after taking informed consent on an informed consent form (ICF) as approved by the PAHS IRC. All patients will be provided written information about the study in Nepali language before enrollment. For patients who

DEFINe Project Principal Investigator: [name]

are unable to understand Nepali, either a family member or a hospital staff will be used as an interpreter to overcome the language barrier and to help the patient understand the study process and its potential harms and benefits.

This project will have equal opportunities for inclusion of women and minorities. Children will be excluded because of a different spectrum of infectious agents outside the scope of this study.

All personal data collected for the study will be stored in a confidential manner in a secure computer with password protection. Only the research team and assigned data analyst will have access to the database. Any new information received during the study will be revealed to the patient. Patients enrolled in the study will be able to withdraw their consent at anytime they wish. Any serious adverse events will be reported to the IRC.

**Registration:** After IRC approval, this study will be registered at Clinical Trial.gov.

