# C. Clinical and Laboratory Questionnaire (Standard of Care Evaluation for all participants)

No.	Questions/ Variables	Data / value	Unit
	BASELINE CLINICAL DATA		
C1	Duration of fever	No. of days	
C2	Clinical Diagnosis		
C3	System involvement	RTI, GI, UTI, CVS, CNS,	
		SSTI, Blood, Sepsis,	
		Lymphatic, Other	
C4	Comorbidities	None, DM, HTN,	
		COPD/chronic	
		pulmonary dis., CHF,	
		MI, PVD, CLD/Liver	
		failure, PUD, CVA,	
		hemiplegia, dementia,	
		CTD, AIDS, solid	
		tumor, lymphoma,	
		leukemia, other	
C5	Temperature in Celsius (baseline at		Celcius
	presentation)		
C6	BP (baseline at presentation)		mmHg
C7	Pulse (baseline at presentation)		per min.
C8	Resp rate (baseline at presentation)		per min.
C9	SaO2 (baseline at presentation)		%
C10	WBC (baseline at presentation)		per cumm
C11	ANC (baseline at presentation)		per cumm
C12	ALC (baseline at presentation)		per cumm
C13	AEC (baseline at presentation)		per cumm
C14	Hgb (baseline at presentation)		g/dL
C15	Plt		per cumm
C16	CRP		
C17	ESR		per hour
C18	Cr		
C19	ALT		
C20	AST		
C21	UA: pus cells		
	MICROBIOLOGICAL DATA		
M1	Blood culture result	Organism name	
M2	Urine culture result	Organism name	
M3	Sputum culture result	Organism name	
M4	Pus culture	Organism name	
M5	GeneXpert	Positive/negative	
M6	Dengue serology	NS1, IgM, IgG	
M7	Scrub typhus	Positive/negative	

M8	Malaria RDT	P falciparum, P vivax,
		other
M9	Kala Azar	Positive/negative
M10	Brucella	Positive/negative
M11	MTB	Positive/negative
M12	Leptospirosis	Positive/negative
M13	Hepatitis A	IgM
M14	Hepatitis E	IgM
M15	Hepatitis B	HBsAg
M16	Hepatitis C	HBC Ab
M17	HIV	
M18	Other test results ()	
M19	Other test results ()	
M20	Other test results ()	
	RADIOLOGICAL DATA	
R1	X-ray finding	Consolidation,
		Infiltrates, Pleural
		effusion, CHF, ARDS,
		other
R2	CT Chest	Consolidation,
		Infiltrates, Pleural
		effusion, CHF, ARDS,
		other
R3	CT Abdomen	Hepatomegaly,
		pancreatitis,
		Cholecystitis, Gall
		stone, Ascites,
		appendicitis, typhlitis,
		intrabdominal
		abscess,
		lymphadenopathy,
		other
R4	USG Abdomen	Hepatomegaly,
		pancreatitis,
		Cholecystitis, Gall
		stone, Ascites,
		appendicitis, typhlitis, intrabdominal
		abscess,
		lymphadenopathy, other
R5	CT/MPI ckull	
KO	CT/MRI skull	Abscess, Meningitis,
		Encephalitis,
		parameningeal focus, other
		otilei

R6	Echocardiogram	Valvular vegetation,
		Pericardial effusion,
		other
	ADDITIONAL SEROLOGICAL EVALUATIONS	Results
	(for Group B patients only)	
D1	Murine typhus	Positive, negative, NA

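### Aim 4 needs the clinician's suspected category and a pre-test probability, but the protocol records neither before the added results, only one open diagnosis field copied from the chart or obtained by patient interview

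*Protocol*

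**What the plan says.** The fourth specific aim in section 4.B (secondary) is: "To estimate the correlation between clinical diagnosis with laboratory diagnosis in patients with undifferentiated fever". Section 5.j, item 5, makes this operational: a pre-test probability for the clinical diagnosis and a post-test probability after the laboratory diagnosis are to be calculated and "correlated for bacterial, rickettsial, viral infections versus other causes of fever". The later text of section 5.j adds that standard calculations and Fagan's nomogram will be used.

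The source of the clinical side is in section 5.h: the "initial clinical diagnosis will be transferred from patient's chart, or by interviewing patients". The same sentence covers the physical examination, and it makes the interview a fallback on a standard questionnaire. In Appendix 1, section C, the diagnosis is item C2, "Clinical Diagnosis". This item sits under the baseline heading but has no response categories, date or probability. The next item, C3, records the organ system involved, not the type of cause.

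Eligibility (section 5.c) requires: "No obvious diagnosis found on the basis of clinical, radiological, or initial routine laboratory tests". Of febrile inpatients with neither localising features nor a laboratory diagnosis, section 2 (preliminary work) says: "These cases are labelled as undifferentiated fever and receive empirical treatment with two or more antimicrobial agents". Section 5.f repeats that fevers not explained by routine tests are generally given this label.

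**The concern.** Aim 4 asks how well clinical judgement anticipates the laboratory answer. That requires the clinician's judgement, in the aim's own four categories and with a probability attached, fixed before the added results are known. The protocol collects none of this directly. It relies on whatever the chart says, in a population selected for having no obvious diagnosis.

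Where the chart carries only the undifferentiated-fever label, the entry cannot be assigned to bacterial, rickettsial or viral, even if the clinician had a firm and correct suspicion. The comparison then measures what was written down and how the analyst codes the label, not how well clinicians judge. The interview fallback does not help, because a patient cannot supply a clinician's diagnosis or a physical examination.

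This is a gap in data capture. A statistical analysis plan can set coding rules for C2, but it cannot recover a pre-result judgement that nobody recorded.

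**Working it through.** **No figure to reproduce.** The sample-size section gives calculations under aims 1, 2, 3 and 5. It states no size, agreement level or precision for aim 4.

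**Needed against collected**

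- *Needed (section 5.j):* a clinical category (bacterial, rickettsial, viral, other) and a pre-test probability. Even if the pre-test probability is meant at group level, as the share of patients clinically assigned to each category, every patient still needs an assigned category.
- *Collected (Appendix 1):* C2 is open text and C3 is organ system. Section E lists antimicrobials given, which is a poor proxy for suspicion because section 2 says these cases receive two or more agents. No item records a suspected category, a ranked differential or a probability.
- *Timing:* C2 has no date. In Appendix 1 the randomisation block comes before the clinical questionnaire.

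**How much the label could matter.** All inputs here are assumptions, because the documents give none of them.

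- u: share of charts with only the label, 0% to 100%.
- c: probability that the remaining charts name the correct category, 0.5 or 0.7. Errors are spread equally over the other three categories.
- Laboratory mix (bacterial/rickettsial/viral/other or none): 15/15/20/50% or 10/10/10/70%.
- Label-only charts are coded as other.

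With p_o the observed agreement and p_e the sum over categories of the products of the row and column margins, kappa = (p_o − p_e)/(1 − p_e). Among laboratory-positive patients, agreement is (1 − u) × c.

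Worked case: u = 0.5, c = 0.7, first mix.

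- p_o = 0.5 × 0.5 × 0.7 + (0.5 × 0.5 + 0.5 × 0.5 × 0.7) = 0.175 + 0.425 = 0.60.
- The clinical margins are 0.095, 0.095, 0.11 and 0.70, so p_e = 2 × 0.15 × 0.095 + 0.20 × 0.11 + 0.50 × 0.70 = 0.4005.
- kappa = (0.60 − 0.4005)/0.5995 = 0.33.
- Agreement among laboratory-positive patients = 0.5 × 0.7 = 0.35.

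Ranges over both mixes and both values of c:

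| Label-only share u | kappa | Agreement among laboratory-positive, (1 − u) × c |
|---|---|---|
| 0% | 0.24 to 0.57 | 0.50 to 0.70 |
| 25% | 0.21 to 0.46 | 0.38 to 0.53 |
| 50% | 0.17 to 0.33 | 0.25 to 0.35 |
| 75% | 0.10 to 0.19 | 0.13 to 0.18 |
| 90% | 0.04 to 0.09 | 0.05 to 0.07 |
| 100% | 0 | 0 |

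**How much the coding could matter.** Take u = 75%, c = 0.7 and the first mix.

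- Label coded as other: raw agreement is 0.5 × 0.25 × 0.7 + (0.5 × 0.75 + 0.5 × 0.25 × 0.7) = 0.55.
- Label counted as no match: 0.25 × 0.7 = 0.175.
- Label-only patients left out: 0.70, but on a quarter of the patients, at most about 0.25 × 117 = 29 in the additional-testing arm.

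Clinician skill is the same in all three. At u = 100%, raw agreement is 0.50 or 0.70 with the first coding, which is simply the share of laboratory results in the other-or-none row. With the second coding it is 0.

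**The case against.** The strongest reply is that the protocol does not say the charts are empty of clinical opinion. Sections 2 and 5.f say how such cases are labelled, or generally labelled, and do not describe everything in the chart. Section 2 also says clinicians treat on decisions drawn from clinical features, which fits a working suspicion being written down. Section 5.h asks for the initial diagnosis, which may precede the label, and having no obvious diagnosis is not the same as having no suspected one. Interview is only a fallback, coding rules for free text often sit in an analysis plan, and aim 4 is secondary.

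Most of this stands, and it rules out three stronger readings that a reader might infer.

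- *That clinical–laboratory agreement must be near zero by construction.* That follows only if nearly every chart carries the label alone, and the documents do not give that share. Aim 4 is also planned as pre-test and post-test probabilities, not as an agreement statistic.
- *That agreement cannot exceed the share of charts with a usable diagnosis.* This fails once label-only charts are coded as other, because laboratory-negative patients then count as agreeing.
- *That serology results will leak into the clinical diagnosis of the additional-testing group.* Section 6 says "Any new information received during the study will be revealed to the patient", and C2 is undated, so a late interview could return a study result. No passage describes that sequence, however. C2 sits under the baseline heading, and the order of the form does not show when a diagnosis was made.

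What the reply does not answer is the missing field. If clinicians do hold working suspicions, the form never asks for them in the categories that aim 4 uses.

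**Conclusion.** The point holds as a gap in data capture for a secondary aim. Aim 4 has no prospectively recorded clinician category or pre-test probability, and patients charted only as undifferentiated fever contribute no information on clinical judgement. The result will therefore depend partly on charting habit and on an unstated coding choice.

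The size cannot be fixed from the documents. It runs from small, if few charts are label-only, to complete, with kappa 0 if all are. The intermediate values rest on the assumed laboratory mix, the assumed accuracy of 0.5 to 0.7, and coding the label as other. Kappa is used only to show the sensitivity and is not the protocol's planned statistic. The protocol should be changed, because a judgement not captured before the added results cannot be reconstructed later without hindsight.

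**What to change.** Add to the baseline form an item completed and time-stamped by the treating clinician before randomisation and before any additional serology result. It should hold:

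- a forced-choice working category (bacterial, rickettsial, viral, other);
- the clinician's probability for that category;
- the leading suspected infection.

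Name this item in section 5.j as the clinical side of aim 4. In section 5.h, remove patient interview as a source for the clinical diagnosis and the physical examination.

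The cost is one form field, a short protocol amendment and about one minute of clinician time per patient: 234 × 1 = 234 minutes, or just under four hours over the whole trial. No extra staff or procedure is needed. The limitation is that patients already enrolled would lack the field. For them, aim 4 can rest only on C2 and should be reported separately, with the number charted only as undifferentiated fever.
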